#### **4.3.3 Subject Exclusion Criteria**

The subject must be excluded from participating in the trial if the subject:

1. Is currently participating and receiving study therapy or has participated in a study of an investigational agent and received study therapy or used an investigational device within 4 weeks of the first dose of treatment.
2. Has a diagnosis of immunodeficiency. Note that patients should not receive steroids during Pembrolizumab administration.
3. Has a known history of active TB (Bacillus Tuberculosis)
4. Hypersensitivity to pembrolizumab or any of its excipients.
5. Has had a prior anti-cancer monoclonal antibody (mAb) within 4 weeks prior to study Day 1 or who has not recovered (i.e.,  $\leq$  Grade 1 or at baseline) from adverse events due to agents administered more than 4 weeks earlier.
6. Has had prior chemotherapy, targeted small molecule therapy, or radiation therapy within 2 weeks prior to study Day 1 and who have not recovered adequately from this treatment ( $\leq$ Grade 2 toxicity at the time of enrollment).
7. Has a known additional malignancy that is progressing or requires active treatment. Patients with a stage I-III cancer that has been cured over two years ago are *not* excluded in the study.
8. Has known active central nervous system (CNS) metastases and/or carcinomatous meningitis. Subjects with previously treated brain metastases may participate provided they are stable (without evidence of progression by imaging for at least four weeks prior to the first dose of trial treatment and any neurologic symptoms have returned to baseline), have no evidence of new or enlarging brain metastases, and are not using steroids for at least 7 days prior to trial treatment. This exception does not include carcinomatous meningitis which is excluded regardless of clinical stability.
9. Has active autoimmune disease that has required systemic treatment in the past 2 years (i.e. with use of disease modifying agents, corticosteroids or immunosuppressive drugs). Replacement therapy (eg., thyroxine, insulin, or physiologic corticosteroid replacement therapy for adrenal or pituitary insufficiency, etc.) is not considered a form of systemic treatment.
10. Has a history of (non-infectious) pneumonitis that required steroids or current pneumonitis.

11. Has an active infection requiring systemic therapy.
12. Has known psychiatric or substance abuse disorders that would interfere with cooperation with the requirements of the trial.
13. Is pregnant or breastfeeding, or expecting to conceive or father children within the projected duration of the trial, starting with the pre-screening or screening visit through 120 days after the last dose of trial treatment.
14. Has a known history of Human Immunodeficiency Virus (HIV) (HIV 1/2 antibodies).
15. Has known active Hepatitis B (e.g., HBsAg reactive) or Hepatitis C (e.g., HCV RNA [qualitative] is detected).
16. Has received a live vaccine within 30 days of planned start of study therapy.
17. Evidence of interstitial lung disease.

*Note: Seasonal influenza vaccines for injection are generally inactivated flu vaccines and are allowed; however intranasal influenza vaccines (e.g., Flu-Mist®) are live attenuated vaccines, and are not allowed.*

## **Additional Exclusion Criteria – Cohorts 1**

1. Patients undergoing an EPP. Lung sparing surgeries, such as pleurectomy/decortication, are acceptable.

## **Additional Exclusion Criteria – Cohort 1**

1. Has received prior therapy with an anti-PD-1, anti-PD-L1, or anti-PD-L2 agent.

## **Additional Exclusion Criteria – Cohort 2**

1. Patients in which hemithoracic radiation therapy is planned.
2. Patients who have received EPP for mesothelioma.

## **Additional Exclusion Criteria – Cohorts 1 and 2**

1. Patients with inherited syndromes associated with hypersensitivity to ionizing radiation, specifically **patients with known history of** Ataxia-Telangiectasia, Nijmegen breakage syndrome.

## 4.4 Trial Treatments

The treatment to be used in this trial is outlined below in Table 2

Table 2 Trial Treatment

Drug	Dose/Potency	Dose Frequency	Route of Administration	Regimen/Treatment Period	Use
Pembrolizumab	200 mg X mg/kg	Q3W	IV infusion	Day 1 of each 3 week cycle	Experimental

Note: Patients must initiate treatment with Pembrolizumab within 1 month of the last day of radiation therapy.

### 4.4.1 Dose Selection/Modification

#### 4.4.1.1 Dose Selection

The rationale for selection of doses to be used in this trial is provided in Section 4.0 – Background and Rationale.

Details on preparation and administration of pembrolizumab are provided in the Pharmacy Manual.

#### 4.4.1.2 Dose Modification

Adverse events (both non-serious and serious) associated with pembrolizumab exposure may represent an immunologic etiology. These adverse events may occur shortly after the first dose or several months after the last dose of treatment. Pembrolizumab must be withheld for drug-related toxicities and severe or life-threatening AEs as per Table 3 below. See Section 5.6.1 and Events of Clinical Interest Guidance Document for supportive care guidelines, including use of corticosteroids.

Table 3

Dose Modification Guidelines for Drug-Related Adverse Events (Note that discontinuation of subjects for all toxicities in Table 3 are contingent on the conclusion that they are treatment related.)

# Proprietary Information of MD Anderson

2015-0856

Version 23

Page 17

Toxicity	Hold Treatment For Grade	Timing for Restarting Treatment	Discontinue Subject/Off-Study Criteria (“Unacceptable” Toxicities)
Diarrhea/Colitis	2-3	Toxicity resolves to Grade 0-1.	Toxicity does not resolve within 12 weeks of last dose or inability to reduce corticosteroid to 10 mg or less of prednisone or equivalent per day within 12 weeks.
	4	Permanently discontinue	Permanently discontinue/Off-Study
AST, ALT, or Increased Bilirubin	2	Toxicity resolves to Grade 0-1	Toxicity does not resolve within 12 weeks of last dose.
	3-4	Permanently discontinue (see exceptions below) 	Permanently discontinue/Off-Study
Type 1 diabetes mellitus (if new onset) or Hyperglycemia	T1DM or 3-4	Hold pembrolizumab for new onset Type 1 diabetes mellitus or Grade 3-4 hyperglycemia associated with evidence of beta cell failure.	Resume pembrolizumab when patients are clinically and metabolically stable.
Hypophysitis	2-3	Toxicity resolves to Grade 0-1	Toxicity does not resolve within 12 weeks of last dose or inability to reduce corticosteroid to 10 mg or less of prednisone or equivalent per day within 12 weeks.
	4	Permanently discontinue	Permanently discontinue/Off-Study
Hyperthyroidism	3	Toxicity resolves to Grade 0-1	Toxicity does not resolve within 12 weeks of last dose or inability to reduce corticosteroid to 10 mg or less of prednisone or equivalent per day within 12 weeks.
	4	Permanently discontinue	Permanently discontinue/Off-Study
Hypothyroidism	2-4	Therapy with pembrolizumab can be continued while treatment for the thyroid disorder is instituted	Therapy with pembrolizumab can be continued while treatment for the thyroid disorder is instituted.
Infusion Reaction	3-4	Permanently discontinue	Permanently discontinue/Off-Study
Pneumonitis	2	Toxicity resolves to Grade 0-1	Toxicity does not resolve within 12 weeks of last dose or inability to reduce corticosteroid to 10 mg or less of prednisone or equivalent per day within 12 weeks. Recurrent grade 2 pneumonitis requires discontinuation of pembrolizumab.
	3-4	Permanently discontinue	Permanently discontinue/Off-Study
Renal Failure or Nephritis	2	Toxicity resolves to Grade 0-1	Toxicity does not resolve within 12 weeks of last dose or inability to reduce corticosteroid to 10 mg or less of prednisone or equivalent per day within 12 weeks.
	3-4	Permanently discontinue	Permanently discontinue/Off-Study
All Other Drug-Related Toxicity 	3 or Severe	Toxicity resolves to Grade 0-1	Toxicity does not resolve within 12 weeks of last dose or inability to reduce corticosteroid to 10 mg or less of prednisone or equivalent per day within 12 weeks.
	4	Permanently discontinue	Permanently discontinue/Off-Study
All other Radiation-Related Toxicity by CTCAE v4.0 criteria (cardiac, esophageal, pericarditis, bowel, etc)	3 or greater	Off Study	Off Study

**Note: Permanently discontinue for any severe or Grade 3 drug-related AE that recurs or any life-threatening event.**

 For patients with liver metastasis who begin treatment with Grade 2 AST or ALT, if AST or ALT increases by greater than or equal to 50% relative to baseline and lasts for at least 1 week then patients should be discontinued.

 For patients with Grade 3 transaminitis, will recheck liver enzymes in 1-2 weeks and if the toxicity changes to Grade  $\leq 2$ , patients can remain on study.

 Patients with intolerable or persistent Grade 2 drug-related AE may hold study medication at physician discretion. Permanently discontinue study drug for persistent Grade 2 adverse reactions for which treatment with study drug has been held, that do not recover to Grade 0-1 within 12 weeks of the last dose.

Dosing interruptions are permitted in the case of medical / surgical events or logistical reasons not related to study therapy (e.g., elective surgery, unrelated medical events, patient vacation, and/or holidays). Subjects should be placed back on study therapy within 3 weeks of the scheduled interruption, unless otherwise discussed with Merck. The reason for interruption should be documented in the patient's study record.

### *Management of Radiation Pneumonitis*

Patients who develop Grade  $\geq 2$  pneumonitis will be managed according to standard clinical guidelines. If supportive measures are unsuccessful, and/or if the symptoms persist despite this approach, steroids and a referral to pulmonary medicine will be considered. A standard regimen of prednisone includes 40-60 mg daily x 2 weeks, then tapering over the next 3-6 weeks based on symptom status. Interventions such as hospitalization, intravenous steroids, and oxygen administration will be performed at the treating physician's discretion.

As noted in the Statistical Considerations section below (Section 8.0), the study will be stopped if 3/6 or 6/12 patients develop Grade 3 or higher radiation pneumonitis. If 0/6, 1/6, or 2/6 patients develop this toxicity, the study will continue. No dose de-escalation will be performed because all patients are already receiving the minimal therapeutic microscopic dose of radiation, and therefore any further reductions in treatment intensity are not likely to control the disease (and still carry the risk of toxicity). Furthermore, our institution does not have experience escalating the radiation dose in mesothelioma higher than that described in this study, and thus it is not appropriate to do so in conjunction with Pembrolizumab without first assessing the effect of higher doses of radiation therapy alone (without immunotherapy). The study is thus addressing the question of whether our institution's current radiation regimen for malignant pleural mesothelioma, in both the unresectable and pleurectomy/decortication settings, is safe with Pembrolizumab. In essence, the two regimens that we are testing are those in the two cohorts that we have included, the first being the most aggressive and including the entire hemithorax (Cohort 1), and the second being a much more limited field and including only the region of palliation (Cohort 2). This trial will provide data as to whether the immunotherapy-radiation combination should be further explored in neither context, only the less aggressive scenario, or in both patient populations.

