#### **4.2.3 Rationale for Endpoints**

Given the lack of experience combining radiation therapy for MPM and immunotherapy, the primary endpoint will be high-grade toxicity, defined specifically in Table 3 below. Specifically, the Off-Study Criteria defined in Table 3 are the “Unacceptable” high-grade toxicities in the trial. That is, patients that meet these criteria will be considered as having met the study endpoint and will be taken off study. Patients will be monitored for 4 months after the start of RT. Since RT is approximately 1 month in duration, this monitoring period will include 3 months after the end of RT.

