### **6.1.4 Other Procedures**

#### **6.1.4.1 Withdrawal/Discontinuation**

**Off-Study Criteria.** Patients will remain on study until completion until they: 1) experience a Grade 3 or higher toxicity during radiation therapy (in which case they will be deemed to be non-evaluable), 2) meet the criteria of Permanent Discontinuation/Off-Study Criteria outlined in Table 3 above (evaluable patient), in which case subjects will be followed until **resolution of symptoms**, 3) are lost-to follow-up, 4) elect to come off study, or 5) die.

When a subject discontinues/withdraws prior to trial completion, all applicable activities scheduled for the final trial visit should be performed at the time of discontinuation. Any adverse events which are present at the time of discontinuation/withdrawal should be followed in accordance with the safety requirements outlined in Section 7.2 - Assessing and Recording Adverse Events. Subjects who a) attain a CR or b) complete 24 months of treatment with pembrolizumab may discontinue treatment with the option of restarting treatment if they meet the criteria specified in Section 7.1.5.5. After discontinuing treatment following assessment of CR, these subjects should return to the site for a Safety Follow-up Visit (described in Section 7.1.5.3.1) and then proceed to the Follow-Up Period of the study (described in Section 7.1.5.4).

If a patient comes off study for toxicity, follow-up will still occur through the research team +/- clinical staff for survival purposes, either through clinic visits as clinically warranted or direct patient calls if the patient no longer follows up at our institution.

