### **7.2 Statistical Analysis Plan**

We will enroll a total of 24 patients, twelve patients to each cohort consisting of distinct radiation and immunotherapy treatment plans. For each study cohort, treatment-related toxicity is defined in Table 3 above (in the column “Discontinue Treatment/Off-Study Criteria”. Therefore, any patient meeting this criteria will be deemed to have experienced an “unacceptable” toxicity for the purposes of the trial. For each study condition, we plan to enroll 12 patients in cohorts of size 6. All patients will be monitored for at least 4 months from the beginning of RT, before declaring the treatment acceptable for enrolling the next cohort of 6 patients.

Continuous monitoring using the method of Thall [20] will be employed for each study cohort of 12 patients in cohorts of size 6 where each patient is monitored for at least 4 months from the start of RT. We will stop the trial if we have reason to believe that the treatment-related toxicity rate is more than 30%. Using the following probability rule

$$\Pr(\text{rate of treatment-related toxicity 4 months from the start of RT} > 30\% \mid \text{data}) > 0.80.$$

If we determine there is more than a 80% chance that the treatment-related toxicity rate is more than 30%, we will stop the trial. We will assume a beta(0.6, 1.4) distribution for treatment-related toxicity as this prior provides a mean of 30% and a standard deviation of 26.5%. Thus the trial will be stopped if

$$[\# \text{ of patients with treatment-related toxicity 4 months from day 1 of the start of RT} / \# \text{ of patients evaluated}]$$

$$\geq 3/6, 6/12$$

Therefore, we will stop either study cohort if we observe 3 or more treatment-related toxicities in the first 6 patients, or if we observe 6 treatment related toxicities at any time while evaluating all 12 patients. We will suspend accrual while evaluating the first 6 patients to ensure none of

the stopping boundaries have been reached prior to enrolling the final 6 patients of each study cohort. The operating characteristics from this decision rule are shown in Table X and are based on 1000 simulations for each scenario.

Table X. Operating characteristics for toxicity monitoring rule

Treatment-related Toxicity 4 months after start of RX	Probability of Stopping Early	Sample Size Avg
0.10	0.017	11.9
0.20	0.099	11.4
0.30	0.254	10.5
0.40	0.462	9.2
0.50	0.650	8.1

- Operating Characteristics acquired using the Stata command stopbound

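### Section 4.4.1.2 applies the 3/6 and 6/12 stopping boundary to Grade 3+ radiation pneumonitis only, while Section 7.2 applies it to any Table 3 off-study toxicity, so the same six patients can mean both stop and continue

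*Combined protocol and SAP*

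**What the plan says.** **Section 4.4.1.2, Management of Radiation Pneumonitis.** The rule is introduced as a report of the statistical plan: "As noted in the Statistical Considerations section below (Section 8.0"). It then says "the study will be stopped if 3/6 or 6/12 patients develop Grade 3 or higher radiation pneumonitis", followed by "If 0/6, 1/6, or 2/6 patients develop this toxicity, the study will continue". The second sentence carries no condition about other toxicities.

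**Section 7.2.** For each cohort, "treatment-related toxicity is defined in Table 3 above", in the column of off-study criteria, and "we will stop either study cohort if we observe 3 or more treatment-related toxicities in the first 6 patients", or 6 while all 12 are evaluated. The 30% limit, the 0.80 posterior cut-off, the beta(0.6, 1.4) prior and Table X are all given for this composite event, counted over 4 months from the start of radiation. Section 7.2 contains no rule for pneumonitis alone.

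**Section 4.2.3.** The endpoint matches Section 7.2: "the primary endpoint will be high-grade toxicity, defined specifically in Table 3 below".

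**Table 3.** Besides pneumonitis, the off-study column covers colitis, hepatic, hypophysitis, hyperthyroidism, infusion, renal and other drug-related events. A further row, "All other Radiation-Related Toxicity by CTCAE v4.0 criteria (cardiac, esophageal, pericarditis, bowel, etc"), takes patients off study at Grade 3 or greater.

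**Section 6.1.4.1.** Patients leave the study if they "experience a Grade 3 or higher toxicity during radiation therapy (in which case they will be deemed to be non-evaluable"). Which patients count therefore depends on when the toxicity starts.

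**The concern.** The same two fractions are attached to two different events. One is a component of the other, and the narrower version comes with an explicit instruction to continue. A team reading Section 4.4.1.2 and a statistician reading Section 7.2 could look at the same six patients and reach opposite decisions about enrolling the next six.

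This is the only numeric safety boundary in a Phase I trial whose primary endpoint is toxicity. Under the Section 4.4.1.2 wording, colitis, hepatitis, nephritis or esophageal toxicity could never trigger it, however many patients were affected. Table X would also not describe that rule. Early termination under Section 4.11 and the six-patient summary to the IND Medical Monitor in Section 7.2 remain available. Neither has a numeric threshold, so neither settles which count governs.

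**Working it through.** **1. Which event the boundary was built for.** Inputs from Section 7.2: prior beta(0.6, 1.4), limit 30%, stop if the posterior probability exceeds 0.80, looks at 6 and 12. With x toxicities in n patients the posterior is Beta(0.6 + x, 1.4 + n − x). Pr(rate > 30%) is:

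| Data | Pr(rate > 30%) | Exceeds 0.80? |
|---|---|---|
| 2/6 | 0.523 | no |
| 3/6 | 0.800003 | yes, only just |
| 5/12 | 0.772 | no |
| 6/12 | 0.905 | yes |

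So 3/6 and 6/12 follow from the Section 7.2 rule, which is written for the Table 3 composite.

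**2. Reproducing Table X.** The chance of stopping at the first look is P(X ≥ 3) with X ~ Bin(6, p). Average sample size is 6·P(stop) + 12·(1 − P(stop)).

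| True rate p | Exact P(stop) | Table X | Exact average N | Table X |
|---|---|---|---|---|
| 0.10 | 0.016 | 0.017 | 11.9 | 11.9 |
| 0.20 | 0.099 | 0.099 | 11.4 | 11.4 |
| 0.30 | 0.256 | 0.254 | 10.5 | 10.5 |
| 0.40 | 0.456 | 0.462 | 9.3 | 9.2 |
| 0.50 | 0.656 | 0.650 | 8.1 | 8.1 |

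Table X therefore describes the six-patient look for the composite. Adding the 12-patient look would give 0.282, 0.519 and 0.747 at 30%, 40% and 50%, which does not match.

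**3. A direct example.** Take six evaluable patients. One has Grade 3 pneumonitis, one Grade 4 colitis and one Grade 3 esophageal toxicity, all treatment-related, starting after radiation ends and within 4 months of its start. Each meets a Table 3 off-study criterion. Section 7.2 counts 3/6 and stops; Section 4.4.1.2 counts 1/6 and continues.

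**4. How often the first six patients would divide the two texts.** Let p be the Table 3 toxicity rate (the Table X scenarios) and s the share of patients with a Table 3 toxicity who have Grade 3+ radiation pneumonitis. The documents give no value for s, so 25%, 50%, 75% and 100% are assumed. Pneumonitis patients are a subset of the toxic patients, so

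P(opposite instructions) = P(X ≥ 3) − P(Y ≥ 3), with X ~ Bin(6, p) and Y ~ Bin(6, p·s).

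For p = 0.30 and s = 0.50: 0.2557 − 0.0473 = 0.2084.

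| p | s = 25% | s = 50% | s = 75% | s = 100% |
|---|---|---|---|---|
| 0.10 | 1.6% | 1.4% | 0.9% | 0% |
| 0.20 | 9.7% | 8.3% | 5.2% | 0% |
| 0.30 | 24.9% | 20.8% | 12.4% | 0% |
| 0.40 | 44.0% | 35.7% | 20.0% | 0% |
| 0.50 | 62.7% | 48.7% | 25.2% | 0% |

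At p = 0.50, Section 7.2 stops at the first look 65.6% of the time. The Section 4.4.1.2 count stops 2.9%, 16.9% or 40.4% of the time for s = 25%, 50% or 75%.

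**5. The reverse conflict.** Section 4.4.1.2 sets no time window and no evaluability condition. Grade 3+ pneumonitis arising during radiation could count there, while Section 6.1.4.1 makes that patient non-evaluable. The table in step 4 leaves this out.

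**The case against.** The best defence is that Section 4.4.1.2 claims no authority of its own. It names the statistical section as its source, and Sections 4.2.3 and 7.2 agree on the composite. Grade 3–4 pneumonitis is itself an off-study event in Table 3. Three treatment-related cases in six evaluable patients within the 4 months would therefore stop the cohort under either text. On this view the pneumonitis paragraph only illustrates the composite rule for one component.

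That makes Section 7.2 the likelier intention, but it does not remove the conflict. The sentence on continuing is unconditional, no clause gives either section precedence, and the paragraph sits with the guidance used to manage toxicity.

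Several limits on the size of the problem do stand:

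- At 10% and 20% toxicity, disagreement is at most 1.6% and 9.7%. The 62.7% figure combines the highest toxicity rate with the lowest assumed share.
- The percentages show how often the texts would disagree. They are not the chance of a wrong decision, which also requires the team to follow Section 4.4.1.2.
- In any actual set of six, the texts agree if three or more have pneumonitis, or if fewer than three have any Table 3 toxicity.
- The pointer to Section 8.0, which is clinical supplies, is editorial. Section 4.4.2 likewise cites the flow chart as Section 6.0 when it is 5.0.
- The stopping unit is mostly clear. Section 7.2 moves from stopping the trial to stopping either cohort, and Sections 2.1, 3.1 and 7.1 call for separate monitoring. The reference to the whole study in Section 4.4.1.2 is the main outlier.

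**Conclusion.** The concern holds. Section 4.4.1.2 misreports the rule it says it is restating, and the plan as written gives two answers to whether the second six patients may be enrolled. The contradiction is in the text and rests on no assumption. Its size does: with pneumonitis at 25% to 75% of patients with a Table 3 toxicity, opposite instructions at the first look have probability 12.4% to 24.9% when the total rate is at the 30% limit, and 25.2% to 62.7% at 50%. The modelled probability is zero only when every counted patient has Grade 3+ radiation pneumonitis. Disagreement is most likely at the higher toxicity rates, where the boundary is most needed. The boundary and Table X need no correction for the composite event.

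**What to change.** Reconcile Sections 4.4.1.2 and 7.2:

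- State once, in Section 7.2, which event is counted and whether reaching the boundary stops the cohort or the study. Which event governs is for the sponsor to say.
- Replace the restated rule in Section 4.4.1.2, including the sentence on continuing at 0 to 2 of 6, with a reference to Section 7.2.
- Correct the cross-reference from Section 8.0 to Section 7.0.
- If a pneumonitis-specific rule is intended as well, give it its own limit and operating characteristics in Section 7.2, and say how it combines with the composite rule. The present prior, 30% limit and Table X are specified for the composite only.

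The cost is a protocol wording change, with no effect on sample size or schedule. A retained pneumonitis rule would add one short operating-characteristics table.

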**Figure 1. IMRT treatment plan with the lung intact.**

Indeed, other reports have also been consistent with these findings. Between 2005 and 2010, 36 patients from Memorial Sloan-Kettering Cancer Center (MSKCC) with malignant pleural mesothelioma who were unable to undergo pneumonectomy underwent induction chemotherapy (89% of patients) and then P/D with adjuvant IMRT (56%) or IMRT with biopsy only (44%). All patients were treated to the pleural surface of the involved hemithorax to a median dose of 46.8 Gy. Seven (20%) patients developed high grade pneumonitis (including 1 death). For patients who underwent PL/D prior to IMRT, the 1- and 2-year survival rate was 75% and 53%, and the median survival was 26 months. For patients who did not undergo surgical resection, the 1- and 2-year survival rate and median survival trended lower at 69% and 28%, and 17 months respectively.[9] These investigators also recently examined patterns of failure when treating the external pleural hemithorax in 67 patients to a similar volume as Figure 2. The rate of in-field local failure was 64%, with 1- and 2-year total failure rates of 56% and 74%, respectively. Interestingly, the authors also found that failure within the fissures was 16%, and only 1 patient had an incisional failure despite the practice of not routinely boosting the incisional sites [10]. Based on these two trials, we have recently completed a prospective study in conjunction with MSKCC examining the efficacy of patients treated with induction chemotherapy, then P/D or no surgery, followed by hemithoracic radiation therapy with IMRT. Thirty nine patients enrolled, and in an interim report 21 patients completed IMRT. Only one patient experienced Grade 3 pneumonitis, a rate below that which is often reported for locally advanced non-small cell lung cancer (NSCLC).[11]

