#### **4.11 Clinical Criteria for Early Trial Termination**

Early trial termination will be the result of the criteria specified below:

1. Quality or quantity of data recording is inaccurate or incomplete
2. Poor adherence to protocol and regulatory requirements
3. Incidence or severity of adverse drug reaction in this or other studies indicates a potential health hazard to subjects
4. Plans to modify or discontinue the development of the study drug

In the event of Merck decision to no longer supply study drug, ample notification will be provided so that appropriate adjustments to subject treatment can be made.

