If the true toxicity rate is 0.50, there is a 65.0% probability of stopping the trial early.

Descriptive statistics will be used to summarize the study data. For each study cohort, we will tabulate toxicities by dose, severity, and relationship to the treatment plan. The method of Kaplan and Meier will be used to estimate median PFS and OS.

A Toxicity/Efficacy Summary will be submitted to the IND Medical Monitor after the first 6 evaluable subjects per cohort, complete 4 months from the initiation of Radiation Therapy and prior to the enrollment of the next cohort, and following the treatment of the next 6 evaluable subjects to each cohort.

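### No enrolment hold is tied to a treatment-related death: the 3/6 and 6/12 boundaries weigh it like any other counted toxicity, and at 2/6 the protocol says the study goes on

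*Combined protocol and SAP*

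**What the plan says.** Section 7.2 sets one rule, applied separately to each cohort: "If we determine there is more than a 80% chance that the treatment-related toxicity rate is more than 30%, we will stop the trial". With the stated prior this becomes 3 of 6 or 6 of 12: "Therefore, we will stop either study cohort if we observe 3 or more treatment-related toxicities in the first 6 patients". The event is any off-study toxicity in Table 3, scored yes or no, with no separate limit for Grade 5.

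The section on managing radiation pneumonitis (4.4.1.2) repeats the same fractions but applies them to Grade 3 or higher radiation pneumonitis. It adds: "If 0/6, 1/6, or 2/6 patients develop this toxicity, the study will continue".

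Other provisions bear on a death:
- Section 7.2 stops recruitment after the sixth patient, whatever the count, until the first six have been followed for 4 months from the start of RT.
- Section 7.2 also provides for a report before the next six enrol: "A Toxicity/Efficacy Summary will be submitted to the IND Medical Monitor after the first 6 evaluable subjects per cohort". It does not say that the monitor must agree before recruitment restarts.
- Section 6.2.3.1 requires reporting within 24 hours, both for deaths from causes other than progression and for unexpected fatal events related to the study drug.
- Section 4.11 lists as a ground for ending the trial: "Incidence or severity of adverse drug reaction in this or other studies indicates a potential health hazard to subjects". No number or time is attached.
- Section 6.1.4.1 lists death as an off-study reason separate from the Table 3 criterion. It also makes patients with Grade 3 or higher toxicity during RT non-evaluable.

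**The concern.** The protocol presents the trial as the first to combine pembrolizumab with radiation in this disease. Its background section cites a 36-patient series of hemithoracic IMRT without pneumonectomy in which "Seven (20%) patients developed high grade pneumonitis (including 1 death"). A limit of 30% is reasonable for a composite made up largely of non-fatal events. It is a coarse instrument for deaths, which would normally prompt a look at a much lower frequency.

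Three gaps combine:
- **Timing.** Section 4.1 foresees one break per arm, at the halfway point. No provision delays patients 2 to 6 after a death in patient 1, or patients 8 to 12 after a death in patient 7. The reporting deadlines carry no consequence for enrolment.
- **Authority.** The monitor receives a summary, but no approval is required. The Section 4.11 criterion is discretionary and speaks of a drug reaction. For a fatal radiation pneumonitis, the continuation sentence in 4.4.1.2 points the other way.
- **Counting.** The pneumonitis row of Table 3 ends at Grade 3-4, and most drug-related rows also end at Grade 4. Together with Section 6.1.4.1, this leaves unclear whether a fatal toxicity, especially one arising during RT, enters the numerator at all.

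**Working it through.** **Inputs.** From Section 7.2: limit 30%, posterior cut-off 0.80, prior beta(0.6, 1.4), looks at 6 and 12. From Section 4.1: 1 pneumonitis death in 36 patients. The documents give no expected treatment-related death rate, so the 10%, 15% and 20% below are assumptions.

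**1. The boundary.** After x events in n patients the posterior is beta(0.6 + x, 1.4 + n − x). Pr(rate > 0.30) is:
- 2/6: 0.523, continue
- 3/6: 0.800003, just over the cut-off, stop
- 5/12: 0.772, continue
- 6/12: 0.905, stop

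The printed 3/6 and 6/12 reproduce.

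**2. Table X.** P(stop at six) = P(X ≥ 3) with X ~ Bin(6, p). Average size = 12 − 6 × P(stop at six).

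| True rate | Stop, printed | Stop, exact | Size, printed | Size, exact |
|---|---|---|---|---|
| 0.10 | 0.017 | 0.016 | 11.9 | 11.9 |
| 0.20 | 0.099 | 0.099 | 11.4 | 11.4 |
| 0.30 | 0.254 | 0.256 | 10.5 | 10.5 |
| 0.40 | 0.462 | 0.456 | 9.2 | 9.3 |
| 0.50 | 0.650 | 0.656 | 8.1 | 8.1 |

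The table is sound, allowing for its 1000 simulations.

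**3. What deaths do to the rule.** Two deaths in six enter as 2/6, giving 0.523 against 0.80, exactly as two non-fatal events would. Two deaths in the first six and three in the next six make 5/12, which reaches neither boundary.

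**4. Worst case: deaths are the only counted events.** P(stop ever) = P(X ≥ 3) + Σ over k = 0 to 2 of P(X = k) × P(Y ≥ 6 − k), with X and Y both Bin(6, p).
- p = 0.10: 0.01585 + 0.00014 = 0.016
- p = 0.15: 0.04734 + 0.00120 = 0.049
- p = 0.20: 0.09888 + 0.00482 = 0.104

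These are lower bounds on stopping at each death rate, because every non-fatal event adds to the count.

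**5. How often a hold after any related death would occur.** P(at least one in n) = 1 − (1 − p)^n.
- p = 1/36: 1 − (35/36)^6 = 0.156; 1 − (35/36)^12 = 0.287
- p = 0.10, first six: 1 − 0.9^6 = 0.469
- p = 0.20, first six: 1 − 0.8^6 = 0.738

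The exact 95% interval for 1/36 is 0.07% to 14.5%. At its ends the chance of a hold is 0.4% to 61% in the first six, and 0.8% to 85% over twelve.

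**The case against.** A reader might infer that two deaths among the first six patients would lead to no pause and no review. The documents do not support that. Recruitment stops after the sixth patient in every case, a summary goes to the IND Medical Monitor before the next six enrol, deaths other than from progression are reported within 24 hours, and Section 4.11 allows termination on severity. What is missing is a pause or review triggered by the death itself.

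A reader might also take the figures in step 4 to mean that the rule gives almost no protection against a high death rate. That does not follow either, because the rule counts a composite. In the cited series there were seven high-grade pneumonitis cases for one death. If that ratio held (an assumption), a 10% death rate would go with about 70% high-grade pneumonitis. The printed rule would then stop with probability 0.98, and 0.93 at the first look. A 5% death rate would go with 35%, and stopping with probability 0.40. The ratio rests on a single death, but it shows that step 4 is an extreme.

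Two further points are fair. The continuation sentence in 4.4.1.2 can be read as a restatement of the boundary, not as an override of Section 4.11. An investigator would also probably count a fatal toxicity as at least Grade 3, as that section's wording for pneumonitis implies. Both readings are sensible, but the text does not secure them. Finally, a single ungraded boundary is an accepted design choice. Nothing here makes the 3/6 and 6/12 rule wrong for its stated purpose.

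What stands: no hold between the scheduled looks, no stated approval before restart, and wording that leaves it uncertain whether every related death counts.

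**Conclusion.** The point holds as a gap in monitoring. The boundaries and Table X are correct for the composite they describe. They treat a related death like any other event, and no other provision ties a death to an enrolment hold. The 1.6%, 4.9% and 10.4% are worst-case figures that assume no non-fatal event is counted and ignore discretionary termination.

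The 1/36 benchmark is weak. It is one pneumonitis death after hemithoracic IMRT, has a wide interval, and says little about limited-field Cohort 2. At exactly 1/36, two or more deaths in six would have probability 1.1%; at the upper limit of 14.5% it would be 21%. The case for a change rests on the missing trigger and its low cost, not on a demonstrated excess risk. It is a worthwhile, inexpensive improvement.

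**What to change.** 1. Reconcile Table 3, the radiation pneumonitis text in 4.4.1.2, Section 4.11, Section 6.1.4.1 and Section 7.2, so that they name the same event and state explicitly that Grade 5 treatment-related events count, including those arising during RT.
2. Add to Section 7.2 that a Grade 5 event judged possibly related to RT, pembrolizumab or both holds new enrolment in that cohort until the IND Medical Monitor has reviewed it and documented the outcome. This applies in addition to 3/6 and 6/12.
3. Make the continuation sentence in 4.4.1.2 subject to that review.

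This governs enrolment only. It changes no dose, no treatment of enrolled patients and no patient-level discontinuation rule.

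**Cost.** A short amendment that uses the existing monitor and existing reporting, plus an occasional accrual pause: about 16% of cohorts in the first six patients and 29% over twelve at an assumed 1/36. Pauses would be more frequent if the true rate is higher or attribution is broad, since the trigger covers any possibly related death and the 1/36 covers pneumonitis deaths only.
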